## 1.2 Rationale

The objective of this extension study is the initial assessment of safety and immunogenicity of the second dose of GBS Trivalent Vaccine following the time interval that is close to the inter-pregnancy interval observed in the general population ([Gemmill](#)

A, Lindberg LD. Short interpregnancy intervals in the United States. *Obstet Gynecol.* 122(1):64-71, 2013).

To address this objective, the subjects who received a single 5µg dose of GBS Trivalent Vaccine or placebo as part of the V98\_06 study, will be vaccinated and receive a second dose of 5µg approximately 4-6 years after the first vaccination. The placebo group from V98\_06 study is included as a control that provides longitudinal data both for the immunogenicity and anti-diphtheria antibodies levels and has the advantage over naive subjects of being a group that was randomized as part of the original study. Naive subjects who have never received GBS Trivalent vaccine will also be enrolled to ensure adequate number of controls in case of significant loss to follow up of the V98\_06 study placebo treated subjects.

While high levels of antibodies to GBS in a pregnant woman are predictive of lower incidence of infant GBS disease, (Lin 2001, Lin 2004, Baker CJ, Kasper DL *NEJM*, 1976), the levels of serotype-specific IgG antibodies needed in a mother in order to protect her infant from GBS have not yet been established. Until these levels have been established, a set of increasing serotype-specific ELISA IgG cut-off levels will be used to attempt to bracket where the assumed protective levels may be. The study objectives are non-specific as to the exact level needed to establish protection.

It is acknowledged that due to loss to follow up the study sample size may be limited. Also, due to baseline heterogeneity of subjects who received different adjuvants or no adjuvant with first vaccination, the study will be exploratory by nature and the results will be interpreted as such.

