### **8.3.7 Subgroups**

Subgroups of subjects will be created based on the ELISA serotype-specific (Ia, Ib, III) antibody LLQ status prior to initial vaccination in study V98\_06 (or V98\_06E1 for the naive group).

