## **8.4 Statistical Analysis Plan**

### **8.4.1 Analysis of Demographic and Baseline Characteristics**

Descriptive statistics (mean, standard deviation, median, minimum and maximum) for age, height and weight at enrolment will be calculated overall and by vaccine group.

Distributions of subjects by sex, race, ethnic origin, V98\_06 vaccine formulation group (or naïve) and pre-vaccination LLQ status will be summarized overall and by vaccine group.

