#### *Geometric Mean Concentrations*

Before any statistical analysis that assumes normally distributed observations, antibody concentrations will be  $\log_{10}$ -transformed. Individual concentrations below the limit of quantitation (LLQ) will be set to half that limit.

The logarithmically (base 10) transformed antibody concentrations will be modeled using an analysis of covariance (ANCOVA) model with a qualitative factor for vaccine group and  $\log$  (base 10) pre-vaccination concentration in study V98\_06, or V98\_06E1 for the naïve group, as a covariate. As this is a single-center study, site is not included as a covariate. Response in the V98\_06 study was different in those with a pre-vaccination concentration below the LLQ, so pre-vaccination concentration is included. The adjusted GMC and the two-sided, 95%, confidence intervals (CIs) of the GMC will be calculated based on this model. The ratio of GMCs and the corresponding two-sided, 95% CI will also be calculated based on this model. The adjusted GMC and two-sided 95% CIs will be constructed by exponentiation (base 10) of the least square means of the logarithmically transformed (base 10) antibody concentration. The model can be written as:

$$\log_{10}(y_{ik}) = \mu + \alpha_i + \beta x_{ik} + \varepsilon_{ik}$$

where  $\mu$  represents a common overall mean,  $\alpha_i$  represents the vaccine group  $i$  effect (where vaccine group is either the V98\_06 vaccine group, or naïve),  $\beta$  represents the common slope for the  $\log_{10}$  prevaccination concentration,  $x_{ik}$  for subject  $k$  in vaccine group  $i$ , and  $\varepsilon_{ik}$  represents random error for subject  $k$  in vaccine group  $i$ . A similar approach will be used in the subgroups based on pre-vaccination LLQ status.

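### The all-subject GBS GMC model adjusts for baseline because response differed below the LLQ, but carries no LLQ term; adding the LLQ indicator already defined in section 8.3.7 is a cheap improvement

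*Combined protocol and SAP*

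**What the plan says.** Section 8.4.3.3.3 (Geometric Mean Concentrations, GBS) gives its reason for baseline adjustment: response in the V98_06 "study was different in those with a pre-vaccination concentration below the LLQ, so pre-vaccination concentration is included". The model has a vaccine-group factor and one covariate, log10 pre-vaccination concentration, taken from V98_06 for returning subjects and from V98_06E1 for naive subjects. Its coefficient "represents the common slope for the" log10 baseline value across all groups. The same section states that "Individual concentrations below the limit of quantitation (LLQ) will be set to half that limit". Adjusted GMCs are back-transformed least-squares means, and GMC ratios with 95% CIs come from the same fit.

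LLQ status appears in three other places. Section 8.3.7: "Subgroups of subjects will be created based on the ELISA serotype-specific (Ia, Ib, III) antibody LLQ status prior to initial vaccination" (in V98_06, or in V98_06E1 for naive subjects). Section 8.4.1: "pre-vaccination LLQ status will be summarized overall and by vaccine group". At the end of the GMC text: "A similar approach will be used in the subgroups based on pre-vaccination LLQ status". It is not a term in the all-subject model.

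On comparability, section 1.2 says that the placebo group "has the advantage over naive subjects of being a group that was randomized as part of the original study".

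**The concern.** The stated reason concerns subjects below the LLQ against those above it, while the model describes baseline by a line. All below-LLQ subjects share one covariate value, so their gap from quantifiable subjects is tied to the slope that also has to fit the subjects above the LLQ. If the true gap departs from that line, two things follow. Unexplained variation goes into the residual and widens every CI. If the below-LLQ share also differs between the groups compared, part of the gap stays in the adjusted GMC ratio as if it were a group effect.

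Unequal shares are possible. Nothing is randomised in this study, the naive subjects are new recruits, and the returning subjects are whoever agrees to come back 4 to 6 years later. At stake is the model-based between-group estimate for all subjects. The variable that would protect it is already derived.

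**Working it through.** **Plan's own figure.** Table 3-1: 5 × 40 + 20 = 220, as stated. Section 8.5 says the size is not based on power, and the documents give no SD, LLQ share or effect size. Everything below on the size of the problem therefore rests on assumptions.

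**When the line is adequate.** Half the LLQ lies at log10(LLQ) − 0.301. With slope b above the LLQ, the line places below-LLQ subjects b × 0.301 under the response at the LLQ. For b = 0.5 that is 0.15 log10. If the true drop is 0.15, the line fits and an indicator gains nothing. A drop of 0.5 to 1.0 is not captured by that slope.

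**Main simulation.** Model as written in section 8.4.3.3.3, with and without an indicator for baseline at or above the LLQ. Assumed: residual SD 0.5 log10, 60% below the LLQ, step of 0.5 or 1.0 log10 at the LLQ, no true group effect, groups of 40 × 5 and 20. Contrast: one V98_06 group against naive, with only the naive share shifted.

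*Equal shares, zero slope above the LLQ.* The linear model is unbiased (ratio 1.00, coverage 94–96%). The indicator cuts the SE by about 2 to 17%, depending on step and on the spread of baseline above the LLQ.

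*Unequal shares, zero slope above the LLQ.* Ratio from the linear model where the true ratio is 1.00, with the naive below-LLQ share higher by 10 / 20 / 30 points:

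| Log10 spread above LLQ | Step 0.5 | Step 1.0 |
|---|---|---|
| Uniform 0–1 | 1.02 / 1.04 / 1.06 | 1.04 / 1.08 / 1.13 |
| Half-normal, SD 1 | 1.04 / 1.08 / 1.12 | 1.08 / 1.17 / 1.25 |
| Exponential, mean 1 | 1.06 / 1.12 / 1.18 | 1.12 / 1.25 / 1.39 |

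With slope 0.3 above the LLQ the range is 1.02–1.35. With a lower naive share it runs from about 0.7 to 0.99. The indicator model gives 1.00 throughout. Coverage of the linear model is 90–96% at shifts up to 20 points and 85–95% at 30 points, against 94–96% with the indicator.

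*Scale.* With the indicator, SE ≈ 0.5 × √(1/40 + 1/20) = 0.137, so the ratio of upper to lower CI limit is about 10^(2 × 1.97 × 0.137) ≈ 3.5. For the linear model it is 3.5 to 4.6. Most of the spurious ratios are small beside that.

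**Second grid.** SD 0.6, slope 0.5, one 5 µg group at 75% below the LLQ against placebo at 45%. The linear model multiplies the GMC ratio by 0.91–0.94 for a drop of 0.6 and by 0.87–0.88 for a drop of 1.0, with coverage down to 92.5%. With the indicator, bias is at most about 0.006 log10.

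**Where the indicator is not the true model.** For a smooth rise above the LLQ to a plateau of 1.0 log10, with the naive share 10–30 points higher, the linear model gives 1.00–1.27 and the indicator 0.99–1.01. For a step of 0.5 in the four primed groups and 1.0 in placebo and naive, they give 1.11–1.60 and 1.08–1.31: reduced, not removed.

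**Cost if the line is right.** Residual df fall from 220 − 7 = 213 to 212, which raises the t quantile by 0.003%. With the naive share equal or up to 30 points higher, the SE rises by 0.2% to about 0.7% at the planned sizes, by up to about 1.2% with 20 per group and by up to about 1.6% with 10 per group. A lower naive share costs slightly more.

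**Least-squares means.** With indicator effect γ and share p below the LLQ, equal weights instead of observed shares shift every adjusted log10 GMC by γ(p − 0.5). For p = 0.6: γ = 0.5 gives 10^0.05 = 1.12, and γ = 1.0 gives 10^0.10 = 1.26. Ratios between groups do not change.

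**The case against.** The strongest case against is that nothing is wrong. Baseline is adjusted for, and substituting half the LLQ gives below-LLQ subjects a lower covariate value, so the slope already absorbs part of the difference. The plan reports GMCs, GMRs, percentages and RCDFs by LLQ status and tabulates that status by group, so a reader can see an imbalance and look within strata. The study has no hypotheses or success criteria and calls itself exploratory. Between groups randomised in V98_06, shares should differ only by chance or selective return, and the larger biases need a large step together with a 30-point imbalance. A common indicator is itself an assumption, because four groups receive a second dose here while placebo and naive subjects receive their first.

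All of this stands as a limit on importance. It does not remove the point: the strata are reported separately, no all-subject estimate combining them is planned, and the model-based ratio with its CI is still to be reported.

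A reader might infer that the linear model is misspecified, or that the reported ratios will be biased. The documents do not support that. A statement that response differed below the LLQ does not establish a step, and bias needs unequal shares as well.

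**Conclusion.** This is a worthwhile, inexpensive refinement of a secondary, descriptive analysis. The gap between the stated reason and the modelled term is real. The harm is conditional: a loss of precision if the line does not fit, and bias only if LLQ shares also differ between the groups compared, for which the naive group is the likeliest case. The sizes depend on assumed SD, step, LLQ share, imbalance and baseline spread, none of which the documents give. The primary day 61 percentages are untouched. It would also be too strong to say that the added term always costs less than 1% of the SE, since that fails with 10 to 20 subjects per group, and section 1.2 warns that numbers may be limited.

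**What to change.** In section 8.4.3.3.3, before analysis:

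1. Add the serotype-specific pre-vaccination LLQ-status indicator from section 8.3.7 to the all-subject GBS GMC ANCOVA, beside log10 baseline: log10(y) = μ + α_i + βx + γ·I(at or above LLQ) + ε.
2. State that least-squares means are evaluated at the observed overall LLQ share, not at equal weights. This affects the adjusted GMCs, not the ratios.
3. Keep the LLQ subgroup analyses, because the common indicator assumes the same LLQ effect in primed and unprimed groups. It would help to note that baseline is constant in the below-LLQ subgroup, so the slope cannot be estimated there and the model reduces to group alone.

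The change needs one model term from an existing variable, one degree of freedom and a few lines of wording, with no new subjects, samples or assays. The precision cost if the straight line is right is the small SE increase given in the working.

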#### *Geometric Mean Ratios*

The logarithmically (base 10) transformed within subject ratio of antibody concentrations (post vaccination / baseline) will be modeled using an analysis of variance model with a qualitative factor for vaccine group (vaccine received in study V98\_06 or naïve). The

adjusted GMR and the two-sided, 95% CIs of the GMR will be calculated based on this model. The model can be written as:

$$\log_{10}(y_{ik}) = \mu + \alpha_i + \varepsilon_{ik}$$

where  $\mu$  represents a common overall mean,  $\alpha_i$  represents the vaccine group  $i$  effect and  $\varepsilon_{ik}$  represents random error for subject  $k$  in vaccine group  $i$ . The baseline value is either the pre-vaccination concentration in study V98\_06 or the pre-vaccination concentration in study V98\_06E1 as both are to be used in separate analyses. A similar approach will be used in the subgroups based on pre-vaccination LLQ status.

### *Anti-diphtheria*

#### *Geometric Mean Concentrations*

The logarithmically (base 10) transformed antibody concentrations will be modeled using an analysis of covariance (ANCOVA) model with a qualitative factor for vaccine group and log (base 10) pre-vaccination concentration in study V98\_06, or V98\_06E1 for the naive group, as a covariate. The adjusted GMC and the two-sided, 95%, confidence intervals (CIs) of the GMC will be calculated based on this model. The ratio of GMCs and the corresponding two-sided, 95% CI will also be calculated based on this model. The adjusted GMC and two-sided 95% CIs will be constructed by exponentiation (base 10) of the least square means of the logarithmically transformed (base 10) antibody concentration. The model can be written as:

$$\log_{10}(y_{ik}) = \mu + \alpha_i + \beta x_{ik} + \varepsilon_{ik}$$

where  $\mu$  represents a common overall mean,  $\alpha_i$  represents the vaccine group  $i$  effect (where vaccine group is either the V98\_06 vaccine group, or naïve),  $\beta$  represents the common slope for the log10 prevaccination concentration,  $x_{ik}$  for subject  $k$  in vaccine group  $i$ , and  $\varepsilon_{ik}$  represents random error for subject  $k$  in vaccine group  $i$ .

#### *Geometric Mean Ratios*

The logarithmically (base 10) transformed within subject ratio of antibody concentrations (post vaccination / baseline) will be modeled using an analysis of variance model with a qualitative factor for vaccine group (vaccine received in study V98\_06 or naïve). The adjusted GMR and the two-sided, 95% CIs of the GMR will be calculated based on this model. The model can be written as:

$$\log_{10}(y_{ik}) = \mu + \alpha_i + \varepsilon_{ik}$$

where  $\mu$  represents a common overall mean,  $\alpha_i$  represents the vaccine group  $i$  effect and  $\varepsilon_{ik}$  represents random error for subject  $k$  in vaccine group  $i$ . The baseline value is either

the pre-vaccination concentration in study V98\_06 or the pre-vaccination concentration in study V98\_06E1 for the naïve subjects.

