**Exploratory Endpoints:**

The exploratory immunogenicity endpoints are:

The serotype-specific (Ia, Ib, and III) geometric mean antibody titer as measured by OPK at days 31 and 61 post-vaccination in study V98\_06E1 in all subjects and by pre-vaccination serotype-specific GBS antibody LLQ status in the V98\_06 study or V98\_06E1 study for the naive group.

The serotype-specific (Ia, Ib, and III) geometric mean antibody titer as measured by OPK at day 1 pre-vaccination in study V98\_06E1 in all subjects and by pre-vaccination serotype-specific GBS antibody LLQ status in the V98\_06 study or V98\_06E1 study for the naive group.

Exploratory OPK objectives will be addressed in a randomly selected subset of up to 60 subjects (10 subjects per arm).

Name of Sponsor: GlaxoSmithKline Biologicals S.A.	Protocol number: V98_06E1	Generic name of study vaccine: GBS Trivalent Vaccine
Statistical Analyses: Statistical Analyses: 
The percentages of subjects with serotype-specific concentrations above a set of pre-defined sequential serotype-specific serum antibody levels and associated two-sided 95% CIs will be computed for each study group on day 1 before vaccination in V98_06E1, and on day 31 and day 61 post-vaccination (primary endpoint). These percentages will be graphically displayed as RCDFs.
 
Additionally, the data will be logarithmically transformed (base 10) before estimating the serotype-specific GMCs at day 1 before vaccination and at day 31 and day 61 post-vaccination. The GMRs, relative to the original baseline and separately relative to the pre-vaccination baseline in V98_06E1 and their associated 95% confidence intervals (CIs) will be computed for each study group.
 
Analyses will be performed for the following groups of subjects:
 

• All subjects

• Subjects determined by their serotype-specific LLQ status prior to initial vaccination in study V98_06 or V98_06E1 for the naive group

• Subjects who received no adjuvant in study V98_06

• Subjects who received alum adjuvant in study V98_06

• Subjects who received half dose of MF59 in study V98_06

• Subjects who received full dose of MF59 in study V98_06

• Subjects who received placebo in study V98_06

• Subjects who are naive and were not vaccinated as a part of V98_06

 
Safety analyses will be performed on the appropriate safety sets.
		

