## **2. OBJECTIVES**

### **2.1 Primary Objective(s)**

#### Immunogenicity Objective

To evaluate the immunogenicity of a second dose of GBS Trivalent Vaccine (5 µg without adjuvant) administered approximately 4-6 years after the initial GBS vaccination, measured by ELISA.

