### **2.2 Secondary Objective(s)**

#### Immunogenicity Objectives

To further characterize the immune response following a dose of GBS Trivalent Vaccine (5 µg without adjuvant) in study subjects and in subgroups of subjects defined by pre-vaccination serotype-specific GBS antibody LLQ status in the V98\_06 study or V98\_06E1 for the naïve subjects.

To assess the impact of a dose of the GBS Trivalent Vaccine (5 µg without adjuvant) on the serum level of anti-diphtheria antibodies in subjects who received study vaccination (active or placebo) as part of the V98\_06 and naïve subjects from V98\_06E1.

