#### **Blood Specimens**

Approximately of 20 mL sample of blood will be drawn from all subjects at visit 1 before vaccination, and at visit 3 and 4. The blood volume will not exceed 25 mL at each time point in order to provide the necessary serum volume (approximately half of the blood draw volume) for the serology assays.

The blood will be used for immunological assays. See [section 7, Assessments](#) for additional details.

The total amount of blood collected over the study period per subject will not exceed 75 mL.

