### **8.1.2.3 Secondary Immunogenicity Endpoint(s)**

The secondary immunogenicity endpoints are:

The percentage of subjects reaching pre-defined sequential serotype-specific (Ia, Ib and III) serum antibody levels as measured by ELISA at other time points and in subgroups of subjects defined by their pre-vaccination serotype-specific GBS antibody LLQ status in the V98\_06 study (or the V98\_06E1 study for the naive group).

The serotype-specific (Ia, Ib, and III) geometric mean concentrations (GMCs) as measured by ELISA at days 31 and 61 post-vaccination in study V98\_06E1 and in the subgroups of subjects defined according to their pre-vaccination serotype-specific GBS antibody LLQ status in the V98\_06 study (or V98\_06E1 study for the naive group).

The within subject geometric mean ratio (GMR) of serotype-specific (Ia, Ib & III) serum antibody levels as measured by ELISA at day 31 and 61. The GMRs will be determined relative to pre-vaccination in V98\_06E1 and separately relative to pre-vaccination in V98\_06 for all groups except the naive group. The GMRs will also be determined for subgroups of subjects defined according to their pre-vaccination serotype-specific GBS antibody LLQ status in the V98\_06 study or V98\_06E1 study for the naive group.

Reverse cumulative distribution function (RCDF) curves of serotype-specific (Ia, Ib and III) serum antibody levels, as measured by ELISA, at pre-vaccination in V98\_06 study or V98\_06E1 study for the naive group, vaccination, day 31 and day 61 post-vaccination in all subjects and by pre-vaccination serotype-specific GBS antibody LLQ status in the V98\_06 study or V98\_06E1 study for the naive group.

The anti-diphtheria geometric mean antibody concentrations measured by ELISA for samples collected before the first vaccination with GBS Trivalent Vaccine in the V98\_06 study or V98\_06E1 study for the naive group and on day 61 post-vaccination in V98\_06E1.

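### In the five groups returning from V98_06, the planned anti-diphtheria GMR starts from a sample about 4-6 years old, so it cannot by itself show the change over the dose given in this study

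*Combined protocol and SAP*

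**What the plan says.** Section 2.2 sets the objective as the impact of one unadjuvanted 5 µg dose "on the serum level of anti-diphtheria antibodies in subjects who received study vaccination (active or placebo) as part of the" V98_06 study, and in naive subjects. Three later passages fix the sample that represents the level before the dose:

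- **Endpoint, section 8.1.2.3:** "The anti-diphtheria geometric mean antibody concentrations measured by ELISA for samples collected before the first vaccination with GBS Trivalent Vaccine" in V98_06 (V98_06E1 for the naive group), and at day 61.
- **ANCOVA for diphtheria GMCs, section 8.4.3.3.3:** the model takes the "pre-vaccination concentration in study V98\_06, or V98\_06E1 for the naive group, as a covariate".
- **GMR for diphtheria, section 8.4.3.3.3:** the baseline is "the pre-vaccination concentration in study V98\_06 or the pre-vaccination concentration in study V98\_06E1 for the naïve subjects".

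For GBS antibody, the GMR paragraph of the same section names both the V98_06 and the V98_06E1 pre-vaccination values, "as both are to be used in separate analyses". The diphtheria paragraph has no such clause.

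The second dose is "administered approximately 4-6 years after the initial GBS vaccination" (section 2.1). Under section 3.5, a "sample of blood will be drawn from all subjects at visit 1 before vaccination". Section 5.1.2 records diphtheria-containing vaccines received between the two studies.

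**The concern.** An objective about the effect of a dose on antibody calls for a comparison across that dose. For returning subjects the planned ratio instead spans the whole interval since V98_06, so a value above or below 1 could reflect the intervening years rather than the V98_06E1 injection.

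Section 1.1 explains why this matters: the carrier, CRM197, is a nontoxic variant of diphtheria toxin, and the protocol says its impact on existing anti-diphtheria levels must be evaluated. For a dose given in V98_06E1, the existing level is the day 1 level. That value is not a planned diphtheria endpoint or baseline in the returning groups.

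**Working it through.** **1. Who is affected.** Table 3-1 allows up to 40 subjects in each of five V98_06 groups, plus 20 naive subjects.

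- Old baseline: up to 5 × 40 = 200 of 220 (91%).
- Given a second GBS dose (the four active groups): up to 4 × 40 = 160.

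**2. The planned baselines side by side.**

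| Analysis | Returning groups | Naive group |
|---|---|---|
| GBS GMR | V98_06 and, separately, V98_06E1 day 1 | V98_06E1 day 1 |
| Diphtheria GMC, ANCOVA covariate | V98_06 | V98_06E1 day 1 |
| Diphtheria GMR | V98_06 | V98_06E1 day 1 |

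The diphtheria GMR paragraph does not name its post-vaccination time; day 61 comes from section 8.1.2.3.

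**3. What the ratio contains.** On the geometric mean scale,

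day 61 / V98_06 baseline = (day 1 / V98_06 baseline) × (day 61 / day 1).

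Only the second factor is the change over the dose, and only the product is planned. The first factor holds waning, diphtheria vaccines received between the studies and, in the active groups, the first GBS dose. Receipt of those vaccines is recorded but enters neither model.

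**4. How far the first factor could move the result.** The documents give no diphtheria levels, decay rates or booster uptake. The rates below are assumptions that show the mechanism; they are not estimates.

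*Waning alone, dose without effect.* GMR = (1 − d)^t, for annual decay d over t years:

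| d | t = 4 | t = 5 | t = 6 |
|---|---|---|---|
| 0% | 1.00 | 1.00 | 1.00 |
| 3% | 0.89 | 0.86 | 0.83 |
| 5% | 0.81 | 0.77 | 0.74 |
| 10% | 0.66 | 0.59 | 0.53 |

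Parameterised instead by half-lives of 5 to 30 years, 0.5^(t / half-life) over 4-6 years gives 0.44 to 0.91.

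*Waning that hides a real rise.* A true f-fold rise from day 1 to day 61 reads as 1.0 or less when d is at least 1 − f^(−1/t):

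| f | t = 4 | t = 5 | t = 6 |
|---|---|---|---|
| 1.25 | 5.4% | 4.4% | 3.7% |
| 1.5 | 9.6% | 7.8% | 6.5% |
| 2 | 15.9% | 12.9% | 10.9% |

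*Boosters alone, no decay, dose without effect.* If a share b of subjects keeps a k-fold rise, GMR = k^b. A GMR of 1.5 needs b = ln(1.5)/ln(k): 17.6% for k = 10 and 25.2% for k = 5.

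The distortion can go either way, and it is nil at zero decay with no boosters. Without a day 1 value these cases cannot be told apart.

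**5. Whether another analysis supplies the missing factor.**

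- The synopsis (Statistical Analyses) plans GMRs "relative to the original baseline and separately relative to the pre-vaccination baseline in" V98_06E1. That sentence follows the one on serotype-specific GMCs and names no diphtheria value. The GMR endpoints in the synopsis and in section 8.1.2.3 are specific to serotypes Ia, Ib and III.
- The day 61 GMC ratio of primed to placebo groups is valid, but it estimates the added effect of an earlier dose. Every group is injected in V98_06E1 (section 3.1), so it does not estimate change over the current dose.
- The naive GMR does run from day 1 to day 61, but for a first dose in 20 subjects. It also sits in one ANOVA with ratios spanning years, so naive and returning GMRs are not like for like.

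**The case against.** The strongest reply is that the long baseline was chosen deliberately. The endpoint, the ANCOVA and the GMR agree on it. Section 1.2 values the V98_06 placebo group for its longitudinal anti-diphtheria data and its original randomization. The description of changes shows that the sponsor revisited this endpoint, removed day 31 and left the baseline alone. Change from before the first dose to after the second, set against placebo, is a coherent target for a concern about repeated CRM197 exposure. Waning and booster use common to the returning groups should largely cancel in that contrast. On this view a day 1 ratio is an extra estimand and not a correction, and the diphtheria GMR is not itself a listed endpoint.

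Much of this stands, and it is why the existing analyses should be kept. It does not answer the objective as worded, which concerns an unadjuvanted dose, the one given in this study. A between-group contrast removes shared drift but also removes the shared effect of that dose.

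Three further points limit the finding:

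- Read literally, section 8.1.2.3 could mean V98_06E1 day 1 for placebo subjects, whose first GBS dose is in this study. The methods text gives that baseline to naive subjects only, so five groups is the better reading. The count that does not depend on this is the four active groups, up to 160 subjects.
- The protocol refers to further detail in a statistical analysis plan. The statement that no such estimate is planned covers the text available here.
- The added ratio would have no undosed control.

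**Conclusion.** The concern holds. As written, the anti-diphtheria GMR in the returning groups cannot by itself show the impact of the V98_06E1 dose, and for subjects given a second GBS dose nothing else planned gives the change from just before it to day 61. The conclusion rests on the text and on the identity in step 3, not on the assumed rates. Those rates show only that the distortion could be material in either direction; its actual size is unknown.

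The stakes are limited. The study is exploratory, its analyses are descriptive (section 8.4.3.3.1), and no primary endpoint is touched. It should still be fixed, because the serum is already drawn and the same two-baseline approach is already planned for GBS antibody.

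**What to change.** Assay anti-diphtheria IgG on the V98_06E1 day 1 serum of the five returning groups, then make three text changes:

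- **Section 8.1.2.3:** add the diphtheria GMC at V98_06E1 day 1, before vaccination, for all groups.
- **Section 8.4.3.3.3, diphtheria GMRs:** keep the present text and add, for example: *In a separate analysis, the V98_06E1 pre-vaccination concentration is the baseline for all groups.* Report the resulting day 61/day 1 ratio as an uncontrolled pre-post change.
- **Synopsis:** carry the same day 1 wording.

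Keep the V98_06-baseline ANCOVA and GMR as the long-term analyses.

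The cost is up to 200 extra ELISA determinations at the external laboratory and a sentence in each of the three places. The naive day 1 sample is already to be tested, no extra blood is drawn, and no existing analysis is lost.
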